4 STUDY DESIGN

This Phase 1/2 study comprises 3 groups in a randomized, placebo-controlled, double-blind clinical trial design. Subjects will be healthy adults, aged 18 through 65 years, with gingivitis as defined by MGI \geq 2.0. The treatment group (1.0 μ M BLXA4-ME oral rinse) and the placebo rinse group will each consist of 50 subjects. The no-rinse control group will consist of 25 subjects. The group sizes allow for a 20% dropout rate.

The treatment group will receive the active agent BLXA4-ME at a concentration of 1.0 μ M in an oral rinse applied once daily (after morning teeth brushing) for 28 days. The placebo rinse control subjects will rinse once daily after morning teeth brushing with the same rinse formulation, except that it will not contain BLXA4-ME. The no-rinse control group will use no oral rinse to assess the effect of the rinsing action independent of the active ingredients. At the Enrollment/Baseline Visit, eligible individuals will be randomly assigned to 1 of the 3 treatment groups. The baseline clinical measurements, i.e., MGI, probing depth (PD), CAL, PI, and BOP, will be recorded. Plaque, GCF, and blood will be collected as described in the Manual of Procedures. The subjects randomized to rinse groups will be given the BLXA4-ME oral rinse formulation or

placebo rinse with instructions for use in addition to their regular oral hygiene. Subjects in all groups will be instructed to maintain their regular oral hygiene procedures, except for using the study-provided rinse, if applicable.

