9.3.1 Relationship to Study Intervention

The clinician's assessment of an AE's relationship to test article is part of the documentation process, but it is not a factor in determining what is or is not reported in the study. If there is any doubt as to whether a clinical observation is an AE, the event should be reported. All AEs must have their relationship to study product assessed using the following terms:

- Related (possible, probable, definite) events meet 1 or more of the following criteria:
 - The event is known to occur with the study intervention.
 - There is a temporal relationship between the intervention and event onset.
 - The event abates when the intervention is discontinued.
 - The event reappears upon a rechallenge with the intervention.
- Not related (unlikely, not related) events meet 1 of the following criteria:
 - There is no temporal relationship between the intervention and event onset.
 - An alternate etiology has been established.

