2.2 Overall Study Design and Plan

This study has a randomized parallel placebo-controlled double-blind study design with one treatment arm and two control arms (placebo oral rinse, and no rinse controls). Subjects in the treatment (N=50) and placebo rinse (N=50) arms will be double-blinded and receive oral rinse (BLXA4-ME or placebo rinse) to be applied once daily after morning teeth brushing. The no-rinse control arm (N=25) will be blinded from the investigators and apply no oral rinse. Subjects will perform their randomized treatment for 28 days. Safety parameters will be assessed before treatment and at Days 3, 7, 14, 21, and 28 after the initial treatment. Efficacy parameters will be assessed before treatment and Day 14 and Day 28 after the initial treatment. Total duration of subject participation will be 3 months (in clinic visits through 28 days, and a follow-up safety phone call at 2 months after last product use).

The Study Flow Chart and the Schedule of Events can be found in Appendices 13.1 and 13.2, respectively.

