3. GENERAL ANALYSIS AND REPORTING CONVENTIONS

The following is a list of general analysis and reporting conventions to be applied for this study. If departures from these general conventions are present in the specific evaluations section of this SAP, then those conventions will take precedence over these general conventions.

- All analysis will be performed using the SAS System version 9.4 or later.
- All subject data listings and summary listings will be sorted for presentation in order of treatment group and subject number in the following order: BLXA4-ME rinse, placebo rinse, and non-rinse control.
- Missing values for both numeric and character variables will be presented as blanks in a table or listing.
- Mixed case will be used for all titles, footnotes, column headers, and programmer-supplied formats.
- All date values will be presented as DDMMYY YYYY (e.g. 21AUG2008) format. A 4-digit year is required for all dates. Partial dates will dashes to represent missing days or months (e.g. - -JUL2009).
- All observed time values will be presented using a 24-hour clock HH:MM format (e.g., 01:35, or 17:26).
- Population sizes will be presented for each treatment group in the column heading as (N=XX).
- The sample size (n) shown as a summary statistic will be the number of subjects with non-missing values.
- Categorical variables will be summarized using counts (n) and percentages (%) and will be presented in the form n (%). All summaries for categorical variables will include all categories, even if none of the subjects had a response in a particular category, to ensure completeness. Continuous variables will be summarized using descriptive statistics: n, mean, median, standard deviation (SD) or standard error (SE), minimum, and maximum. The mean and median will be reported at 1 more significant digit than the precision of the data. The SD and/or SE will be reported at 2 more significant digits than the precision of the data. The minimum and maximum will be reported to the same level of precision as the original observations.
- Calculated variables will not be rounded prior to analysis. Rounding will only occur after analysis. If any values are calculated to have more significant digits than the original data, then the value will be rounded so that it is the same level of precision as the original data.
- P-values will be reported to 3 decimal places if greater than 0.001. If less than 0.001 then p-values will be reported as '<0.001'.

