4.1 Safety Population

The Safety Population will consist of all subjects who are randomized into a study arm and complete their Baseline Visit. For the safety evaluations, subjects will be analyzed according to the treatment actually received. Any subjects that in error were administered both the BLXA4-ME and the placebo rinse at different times during the study will be analyzed in the BLXA4-ME treatment arm. Subjects that in error were administered both the non-rinse control treatment and either the BLXA4-ME or placebo rinse will be analyzed according to the rinse administered.

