8. SAFETY EVALUATION

8.1 Overview of Safety Analysis Methods

All safety analyses will be carried out using the Safety Population.

- Adverse events (AEs)
- Unanticipated problems
- Vital signs
- Laboratory determinations (hematology, serum chemistry, and urinalysis)
- Physical examinations
- Dental examinations

With the exception of the progression of periodontitis based on the dental examinations, no statistical comparisons between the treatment groups are planned for the safety variables.

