8.4 Adverse Events

All AEs will be coded to a system organ class (SOC) and preferred term (PT) using the most current version of the Medical Dictionary for Regulatory Activities (MedDRA). All tabular AE summaries will be for TEAEs. TEAEs will be defined as those AEs with an onset on or after the date of first dose of study drug (study visit 1: Day 0). If an AE was recorded prior to the first dose of study drug and there was an increase in its severity, the AE will be considered a TEAE. All other AEs will be classified as non-treatment-emergent. Treatment-emergent AEs will be flagged in all AE data listings.

An overall summary table will be developed to report the number of events and the incidence of participants having at least one event in the following categories:

- TEAEs
- TEAEs indicated as serious (SAEs)
- TEAEs that lead to study drug discontinuation
- TEAEs with an outcome of death
- TEAEs that were reported as having a definite/certain or possible relation to study drug
- TEAEs reported as having a severity rating of severe

In addition, a summary table of TEAEs classified by system organ class (SOC) and preferred term (PT) will be provided for each of the following:

- TEAEs
- TEAEs by maximum severity
- TEAEs by relationship to study drug

The summary of all TEAEs will present both the number of TEAEs and the incidence of TEAEs. The summary of TEAEs by severity, relationship to study drug, and week of treatment will only report the incidence of TEAEs. When reporting the number of TEAEs, if the same TEAE occurs for a subject on multiple occasions the event will be counted once for each occurrence. When reporting the incidence, a subject will only be counted once if they ever experience an event within the SOC and ever experience the individual PT.

For the summary of TEAEs by severity, if the severity of the TEAE is not reported, then the severity of the TEAE will be counted as severe. If the same TEAE occurs for a subject on multiple occasions, the TEAE will be categorized according to the highest severity rating for that TEAE in that subject. For the summary of TEAEs by relationship to study drug, if the relationship is missing, it will be counted as definite/certain. If the same TEAE occurs for a subject on multiple occasions, the TEAE will be categorized according to the closest relationship to study drug reported for that TEAE in that subject.

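### SAP 8.4 counts a missing AE relationship as definite/certain without excepting the no-rinse arm, where a relationship to product is impossible

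*SAP*

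**What the plan says.** SAP 8.4 plans a table of TEAEs by system organ class, preferred term and relationship. Its missing-data rule opens "For the summary of TEAEs by relationship to study drug" and continues "if the relationship is missing, it will be counted as definite/certain". No arm is named or excepted.

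The table covers all three arms. SAP 8.1 says "All safety analyses will be carried out using the Safety Population", and SAP 4.1 defines that population: "The Safety Population will consist of all subjects who are randomized into a study arm and complete their Baseline Visit". Having used a product is not a condition. SAP 3 gives the order of groups, for listings, as "BLXA4-ME rinse, placebo rinse, and non-rinse control".

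The third group takes nothing. SAP 2.2: "The no-rinse control arm (N=25) will be blinded from the investigators and apply no oral rinse". Protocol 4: "The no-rinse control group will use no oral rinse".

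On collection, Protocol 9.3.1 says "All AEs must have their relationship to study product assessed using the following terms". The terms fall under related (possible, probable, definite) and not related (unlikely, not related). There is no 'not applicable' term, and no arm is exempt.

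**The concern.** Replacing a missing relationship with the closest category is a common worst-case convention. In a subject who used a rinse it is sensible: the true value is unknown, and the rule avoids understating harm. In a subject who used no product the true value is known. No product relationship exists, and the rule returns the opposite extreme.

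At stake is the accuracy of one table that supports the primary, safety objective. A false definite/certain entry in an untreated column raises that column's related-event incidence, so the default works against its own purpose there. SAP 8.4 also asks for no count of imputed relationships, so an imputed entry could not be told apart from a clinician's rating.

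**Working it through.** The SAP gives no figure on this point, so there is none to reproduce. The check is first logical, then a matter of scale.

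**Can the rule reach a no-rinse subject?**

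1. The by-relationship summary uses the Safety Population (SAP 8.1), which includes the no-rinse arm (SAP 4.1).
2. SAP 8.4 ties a TEAE to the first dose but equates that with Visit 1, Day 0. A no-rinse subject has no first dose but does have a Day 0, so AEs in that arm can be TEAEs.
3. SAP 4.1 moves a no-rinse subject who was given either rinse in error to the arm of that rinse. Those left in the no-rinse column therefore took no product, and a definite product relationship cannot be true for them.
4. The missing-relationship rule has no arm restriction. That it applies to every arm is inferred from this silence; the SAP does not say so expressly.

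So a blank in the no-rinse arm is tabulated as definite/certain.

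**Weight of one affected subject**

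Inputs are the planned arm sizes of 50, 50 and 25, or 40, 40 and 20 after the assumed 20% attrition (SAP 2.5).

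| Denominator | No-rinse arm | A rinse arm |
|---|---|---|
| Randomised | 1/25 = 4.0 points | 1/50 = 2.0 points |
| Completers | 1/20 = 5.0 points | 1/40 = 2.5 points |

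The randomised row fits the Safety Population. Replacement of early withdrawals (Protocol 5.5.2) could make the denominators somewhat larger.

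**Effect on the contrast with BLXA4-ME**

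Let b_A and b_N be the numbers of subjects whose definite/certain entry comes only from imputation in the BLXA4-ME and no-rinse arms. Their contribution to the difference, BLXA4-ME minus no rinse, is:

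- rule as written: b_A/50 − b_N/25
- default limited to the rinse arms: b_A/50

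The first is lower by b_N/25, that is 4 points per no-rinse subject, whatever b_A is. If the comparison is instead with no imputation at all, the rule changes the difference by b_A/50 − b_N/25. That is negative only if the affected share is larger in the no-rinse arm.

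**How likely is at least one false entry?**

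The documents give neither the share of subjects with a TEAE (a) nor the chance that such a subject's relationship is blank (m). With assumed values and n = 25, the chance of at least one is 1 − (1 − a·m)^25 and the expected number is 25·a·m:

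| a | m | Chance of at least one | Expected subjects |
|---|---|---|---|
| 20% | 1% | 1 − 0.998^25 = 5% | 0.05 |
| 50% | 5% | 1 − 0.975^25 = 47% | 0.62 |
| 80% | 10% | 1 − 0.92^25 = 88% | 2.0 |

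The first row fits a rating that is compulsory. The last needs both inputs to be high. With the default limited to the rinse arms, the number is 0 by construction.

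**The case against.** The strongest reply is that the rule may never be used in this arm. Protocol 9.3 and 9.3.1 make the rating compulsory, Protocol 16.1 has the investigator or a designee review AEs, and Protocol 16.2 builds checks into the database. This stands as a limit on size. It does not make the rule right when it is used, and the SAP evidently allowed for some blanks.

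The reach is also narrow. The sentence covers one summary. The overall TEAE table counts relationships as reported, and the missing-data triggers in SAP 8.2 and 9.1.1 refer to relationships as rated, so on their wording an imputed value does not enter them. The affected table is split by preferred term, so several subjects would usually fall in different rows. All of this stands.

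A reader might infer that blanks are more likely in the no-rinse arm, because the scale has no 'not applicable' term and the staff member who dispenses product knows that none was given. The documents do not support that. SAP 2.4 masks the investigator, coordinators and examiners to this arm. Protocol 9.1.1 reserves the rating for those qualified to diagnose, and no section gives it to the dispenser as such. Not related is an available answer.

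A reader might also infer that the rule makes BLXA4-ME look safer in general. That goes too far. AE comparisons are descriptive (Protocol 12.1, SAP 8.1), placebo is the direct comparator for the active ingredient, and the plan ranks the no-rinse arm below the other two (Protocol 12.3). The same default also raises the BLXA4-ME count.

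It can be said that a definite entry under a no-rinse heading exposes itself, that a footnote would suffice, or that the table shells, kept in a separate document (SAP 12), may settle the display. A footnote would help, but it would leave impossible entries in the related rows, and unseen shells do not override an explicit SAP rule. Nor is an arm-specific rule out of keeping: SAP 4.1 already sets several, and in this arm the value is known rather than imputed.

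**Conclusion.** The defect is real and small. When triggered, the rule produces an entry that cannot be true: 4 points of the no-rinse arm per affected subject, with the BLXA4-ME minus no-rinse difference lower by the same amount than under correct handling. The number affected is unknown, should be low and may be zero. Total TEAE incidence, the BLXA4-ME versus placebo contrast, sample size and power are untouched.

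This rests on two readings: that silence about arms means all arms, and that Day 0 serves as the treatment-emergence anchor for subjects with no dose. It concerns missing ratings only. A related rating actually given by a masked clinician to a no-rinse subject is reported data and a separate matter.

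**What to change.** In SAP 8.4:

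- Limit the missing-relationship default to subjects analysed in the BLXA4-ME or placebo rinse arms.
- In the no-rinse arm, show a missing relationship as 'not applicable (no product)', outside the related rows.
- Footnote the by-relationship table with the number of imputed relationships in each arm.

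The cost is one sentence and one footnote. No new data are needed. Blinding is unaffected, because SAP 2.4 breaks the blind after database lock and the rule can be applied by arm from then on.

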8.5 Deaths, Serious Adverse Events, and Other Significant Adverse Events

In addition to these summary tables, the incidence of adverse events leading to death, the incidence of SAEs, and incidence of TEAEs that led to study drug being discontinued will be presented in summary tables and listings. The summary listings will provide all of the information reported for that AE and will include the number of days from date of first dose to date of the occurrence of the AE.

8.6 Clinical Laboratory Evaluation

Subject clinical chemistry, hematology, and urinalysis samples will be obtained at the baseline, Day 14 and Day 28 visits. All lab results will be listed by subject, laboratory parameter, and time. Out-of-range flags (H: high; or L: low) when available will be used to denote abnormal values.

All treatment-emergent abnormal values, as determined on the basis of the normal values provided by the central laboratory, will be listed with relevant subject information. In addition, all treatment-emergent values that were deemed clinically significant (CS) by the on-site medical monitor will be flagged in the listing. An additional listing will only list records whose values were deemed clinically significant.

The quantitative hematology, clinical chemistry, and urinalysis parameters and their change from baseline will be summarized in tables by study arm and study visit. Summary statistics will include n, mean, SD, median, minimum, maximum values, and the number and percent of subjects with missing values for the laboratory test. Repeat or ad hoc laboratory tests will not be summarized, but they will be included in the listings. The order of presentation will cluster the laboratories by test and time of measurement in three tables for clinical chemistry, hematology, and urinalysis data, respectively.

For hematology, clinical chemistry, and urinalysis laboratory parameters, shift tables will be presented for change from baseline at study Day 14 and Day 28. For the shift tables, the Baseline laboratory parameter values will be cross-referenced with their associated study visit Day 14 and Day 28 laboratory parameter values with respect to the n and percent of parameter values flagged as low, normal, high, or abnormal based on the laboratory provided normal ranges for each of the lab parameters. The shift tables will include an extra column for baseline values that shift to missing values due to early withdrawal or otherwise.

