5.1 Subject Inclusion Criteria

1. Signed consent form;
2. Good general health as evidenced by medical history;
3. Age 18 through 65 years;
4. Stable address;
5. Availability for the duration of the study (if a subject does not meet this criterion, he/she may be rescreened for study participation when he/she does meet this inclusion criterion);
6. Minimum of 20 natural teeth, excluding third molars;
7. Mean full mouth MGI of at least 2.0;
8. Willing to use prescribed oral hygiene procedures and products;

9. Stability of medications for chronic conditions for at least 3 months prior to enrollment (if a subject does not meet this criterion, he/she may be rescreened for study participation when he/she does meet this inclusion criterion);
10. For women of reproductive potential, use of licensed hormonal contraception or double-barrier methods;
11. For men of reproductive potential, agreement to use condoms;
12. Liver function test (aspartate aminotransferase [AST], alanine aminotransferase [ALT], alkaline phosphatase, and total bilirubin) levels equal to or less than 1.5 times the upper limit of normal;
13. Serum creatinine levels equal to or less than the upper limit of normal;
14. Subjects with complete blood count levels within 10% of the normal laboratory range and erythrocyte sedimentation rate equal to or less than 2 times the upper limit of normal.

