8.2.1.2 Blood and Urine Analyses for Safety Assessments

Blood will be sent to a clinical laboratory for the following tests:

- Complete blood count: hemoglobin, hematocrit, red blood cell (RBC) count, white blood cell (WBC) count with differential and absolute counts by WBC type, platelet count, and RBC indices (mean corpuscular volume, mean corpuscular hemoglobin concentration, RBC distribution width)
- Erythrocyte sedimentation rate
- Serum chemistry tests: creatinine, blood urea nitrogen, alkaline phosphatase, AST, ALT, total bilirubin, and electrolytes (sodium, potassium, chloride, and bicarbonate).
- Urinalysis: color, appearance, specific gravity, pH, glucose, bilirubin, ketones, occult blood, protein, nitrite, leukocyte esterase, WBCs, RBCs, squamous and other epithelial cells, bacteria, casts, and crystals.

The on-site medical monitor will review the results of safety laboratory tests to determine whether a laboratory test should be redrawn. Subjects with serum creatinine values greater than 50% above their baseline level will be retested, even if within normal range. Subjects with persistent out-of-normal values at the retest will be referred to their primary care physician and will be followed until the values have returned to the normal range or are confirmed as stable with an adequate explanation. Additionally, the on-site medical monitor will review the laboratory results to assist the principal investigator with assessing and monitoring AEs.

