9.5 Rules for Study Suspension or Discontinuation

The NIDCR medical monitor will review all SAEs and UPs in an expedited fashion. In the event of unacceptable toxicity, the trial will be stopped prematurely to prevent harm to subjects. In addition, any injuries, SAEs, or other unexpected AEs involving risk to subjects or others, and occurring at a frequency above that considered acceptable by the investigators, IND sponsor, NIDCR, or IRB, may result in a temporary or permanent halt to the study. The study may be suspended for a safety review and consideration of study discontinuation if:

- One or more subjects experiences a clinically significant event or laboratory abnormality determined to be Grade 3 or higher and related (possibly, probably, definitely) to use of the investigational product;
- Two or more subjects experience a similar event determined to be Grade 2 or higher and related (possibly, probably, definitely) to use of the investigational product;
- One or more subjects experiences a Grade 2 or higher event that does not resolve within 14 days.

The NIDCR medical monitor or DSMB may request to be unblinded to the entire study when evaluating whether to suspend or discontinue the study. In the event of study unblinding, a non-study statistician will be assigned as the “unblinded statistician” to assist in unblinding and any safety review.

Any proposed changes in the consent form or research procedures resulting from any safety findings are to be submitted by the principal investigator to the IRB for approval.

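### The shift tables in SAP 8.6 use normal-range status alone, and no planned table counts by arm the subjects who meet the protocol's creatinine rule or worsen from an already-high value

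*SAP*

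**What the plan says.** SAP 8.6 plans five kinds of laboratory output:

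- A listing of every result, with high and low flags. Repeat tests appear here but are kept out of the summaries.
- A listing of abnormal values: "All treatment-emergent abnormal values, as determined on the basis of the normal values provided by the central laboratory, will be listed".
- A judgement flag: "all treatment-emergent values that were deemed clinically significant (CS) by the on-site medical monitor will be flagged in the listing". A separate listing shows only the values so judged.
- Continuous tables, in which the quantitative "parameters and their change from baseline will be summarized in tables by study arm and study visit". On content: "Summary statistics will include n, mean, SD, median, minimum, maximum values", plus the number missing.
- Shift tables at Day 14 and Day 28, cross-classifying "parameter values flagged as low, normal, high, or abnormal based on the laboratory provided normal ranges".

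The protocol uses finer criteria in three places:

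- Section 8.2.1.2: "Subjects with serum creatinine values greater than 50% above their baseline level will be retested, even if within normal range".
- Section 5.1: creatinine must not exceed the ULN at entry, but liver tests are accepted at "levels equal to or less than 1.5 times the upper limit of normal" and ESR at up to twice the ULN.
- Section 9.5: one possible trigger for suspension is a related "clinically significant event or laboratory abnormality determined to be Grade 3 or higher". Section 9.3.3 names CTCAE v4.0 as the grading scale.

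**The concern.** The shift tables are the only categorical laboratory output, so they are where a reader will look for the number of subjects in each arm whose results got worse. Normal-range categories miss two kinds of worsening that the protocol makes relevant. One is the in-range creatinine rise that the protocol singles out. The other is further deterioration in a subject whom the entry criteria allowed in with a value already above normal.

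Laboratory findings belong to the primary objective (protocol 3.1; SAP 2.1). This is the first human use of the rinse (protocol 9.3.2), and safety blood and urine are collected because the compound may be absorbed through the mucosa (protocol 2.5.1). The laboratory analysis is descriptive, so a difference between arms would have to be seen in counts. If those counts are not tabulated, a pattern of a few subjects in one arm could go unnoticed.

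**Working it through.** SAP 8.6 states no figure on this point, so there is none to reproduce. The check applies its classification rule to the protocol's limits, with values in multiples of the ULN. A value is normal at or below 1.0 and high above 1.0. Starting and ending values are illustrations, not trial data.

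**Creatinine.** Let b be the pre-treatment value (b ≤ 1.0 by the entry criterion) and f a later value. The retest rule is met when f > 1.5 × b. The value stays in range when f ≤ 1.0. Both can hold only if 1.5 × b < 1.0, that is b < 1/1.5 = 0.667. For a rise just over the limit (f = 1.51 × b):

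| b | f | Shift-table cell |
|---|---|---|
| 0.60 | 0.906 | normal-to-normal |
| 0.65 | 0.982 | normal-to-normal |
| 0.70 | 1.057 | normal-to-high |
| 1.00 | 1.510 | normal-to-high |

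A low starting value does not hide every rise: 0.60 doubled is 1.20, which is normal-to-high.

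**Liver tests and ESR.** A subject entering above 1.0 (up to 1.5 for liver tests, 2 for ESR) starts as high, and no category lies above high. A liver test going from 1.2 to 3 (3/1.2 = 2.5-fold), from 1.5 to 5 (5/1.5 = 3.33-fold) or from 1.5 to 10 (10/1.5 = 6.67-fold) reads high-to-high each time.

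**Can the continuous tables supply the count?** They do register both kinds of rise, and a large one may be the arm's maximum. They report absolute change, which does not identify a percentage rule:

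- A change of +0.33 from b = 0.50 is 0.33/0.50 = 66%. It meets the rule, and f = 0.83 is in range.
- The same change from b = 1.00 is 33%. It does not meet the rule, and f = 1.33 is high.

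The shift table therefore flags the second subject and not the first. One subject with this change moves the mean of a 40-subject arm by 0.33/40 = 0.008. A maximum shows the most extreme subject, not how many met the rule.

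**Can the other outputs supply it?**

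- The full listing holds every value, but the reader must work out each ratio and count by arm.
- The clinically-significant flag has no numeric criterion and feeds listings only. SAP 8.6 does not say whether a value already high before treatment can be treatment-emergent. For oral examinations, SAP 8.8.2 requires a normal baseline.
- Retests prompted by the creatinine rule are listed and not summarised.
- The adverse event tables include a laboratory change only if it was recorded as an adverse event.

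**Comparison within the SAP.** Table 8.8.1.1 gives vital signs and weight numeric criteria relative to baseline, such as a heart rate change of at least 30 BPM or a weight change of at least 7%. Laboratory values have no counterpart, although the protocol supplies one for creatinine.

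**The case against.** The plan is coherent for a descriptive analysis of 125 subjects. It lists all results, tabulates change from baseline with the minimum and maximum, and lists values the medical monitor judged clinically significant. Protocol 12.5.1 asks for changes from baseline in laboratory results, and SAP 8.6 provides them. The 50% rule is an instruction to retest, not an endpoint. Protocol 9.1.1 counts an abnormal laboratory finding as a possible adverse event and requires a deteriorating pre-existing condition to be recorded, so a marked liver rise has a route into the tables by severity in SAP 8.4. SAP section 12 keeps the list of tables in a separate document.

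Much of this stands, and it rules out three stronger readings that a reader might infer:

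- *That all the laboratory tables would show no change.* This is true of the shift tables only.
- *That every creatinine rise above 50% is hidden because all subjects start at or below the ULN.* From 0.667 times ULN upward, such a rise crosses the ULN and appears as a shift.
- *That the suspension rules cannot be applied without a graded table.* They operate during the trial, through the medical monitor and the DSMB (protocol 9.5 and section 10), and do not depend on end-of-study tables.

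What the objection does not answer is the missing count. None of the outputs described in SAP 8.6 states how many subjects in each arm met the creatinine rule or worsened beyond an already-high value.

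**Conclusion.** The point holds as a gap in reporting. The shift tables and the treatment-emergent abnormal listing rest on normal-range status, and no table described in the SAP counts either kind of worsening by arm.

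For creatinine, the gap is confined to subjects starting below 0.667 times ULN whose rise stays in range. For liver tests and ESR, it covers subjects who enter above the ULN, whatever the later value. It applies at both post-treatment laboratory visits and in all arms. How many subjects are involved cannot be derived, because the documents give neither the laboratory's ranges nor the distribution of entry values.

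The conclusion assumes that high means above the laboratory's ULN and that the separate list of tables adds no such count. Individual cases can still be found through the other outputs, so this is an inexpensive improvement to a primary-objective safety domain. It does not show that the safety analysis fails.

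**What to change.** Add to SAP 8.6:

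1. The number and percentage of subjects per arm with any post-baseline creatinine more than 50% above the pre-treatment value. Name the screening result as that value, since the schedule of events takes no safety blood on Day 0. State whether repeat tests count. Using the scheduled Day 14 and Day 28 results, with repeats shown in the listing, would match the SAP's existing convention.
2. For analytes that can be graded under the protocol's CTCAE v4.0, a shift table from baseline grade to worst post-baseline grade, by arm. Keep the normal-range shift tables for the rest. The protocol gives only general grade descriptions, so the SAP must specify the laboratory thresholds from that scale. If ESR has no grade there, say so, because its high-to-high limitation then remains.
3. A listing of subjects who meet item 1 or rise by one grade or more.

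The cost is SAP wording and the programming of two tables and a listing from data already collected. The change adds reporting only and leaves clinical management and the suspension rules as they are.
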